Molar Incisor Hypomineralization (MIH) is a systemic origin, qualitative developmental defect of enamel affecting one to four first permanent molars and frequently involving incisors (Weerheijm, 2001). Lesion presented as well-demarcated discolouration of the enamel, or enamel destruction due to breakdown or dental caries with a global prevalence was estimated around 14.2% (Schwendicke F et al, 2018). MIH teeth presented with various clinical problem including increase susceptibility of caries and post eruptive breakdown, inferior bonding to composite restoration, recurrent restorative failure, hypersensitivity, and difficulty to achieve anaesthesia. Extraction of the MIH affected first permanent molar is an option and require comprehensive evaluation and 'ideal' time. Currently, acceptance to invasive restorative treatment and extraction is a significant challenge in children. Hence, a less-invasive treatment using glass ionomer cement (GIC) with remineralisation and desensitising agents that comply with principle of Minimal Intervention Dentistry (MID) has gained attention as interim therapeutic restoration in moderate to severe MIH affected tooth to prevent progression of disease. Silver Diamine is a high concentration topical fluoride agent has shown superior performance for remineralization and caries arrest (Gao et al., 2016). Papain based gel is a chemomechanical caries removal and deproteinizing agent assist to remove debris and protein without the need of rotary instrument(Deng et a., 2018). There is a paucity in the published literature regarding the effect of SDF and papain-based gel on MIH-affected teeth. To date, no study has been done to evaluate the clinical outcome of MIH-affected molars treated with papain-based gel as deproteinising agent and SDF followed by interim therapeutic restoration with GIC. It is hoped that findings obtained from this study will give new insight into managing MIH-affected molars in children

Objective:

The aim of the study is to determine the clinical outcome of additional SDF with and without papain-based gel on MIH molars versus HVGIC alone as interim therapeutic restoration at 6 and 12 months. Specifically, the objective of this study is

1. To determine and compare the clinical outcome determine as success and failure of treatment related to pulpal health, structural integrity and hypersensitivity on MIH molars treated with GIC alone or with or without the use of SDF and papain-based gel at 6 and 12 months

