Sample size: The sample size is calculated based on Grossi et al., who reported that the clinical success of GIC (Equia Forte) restoration using ART technique in MIH affected permanent molars was 98.3% (Grossi et al., 2018). Since there was no literature reporting on the clinical success of Silver Diamine Fluoride and papain-based gel on MIH-affected molars, the success rate was assumed to be 50%. With an estimated error of 5% and power of 90%, the minimum estimated sample size was calculated to be 14 teeth per intervention group. The sample size calculation will be performed using G-power 3.1 software that calculated the power and sample size for tests by comparing two independent binomial populations with probabilities π_1 and π_2 , respectively. Pearson chi-square test was used to test the association of two binary variables (two groups and two outcomes). An additional 50% was added to compensate for the possibility of high dropout or recall failure. Hence, the number was increased to 21 teeth per group for a total of 63 teeth. The high percentage of dropout rate in this study is decided to accommodate a high need of retreatment of GIC restoration based on few published literature (Al Muallem et al., 2018; Linner et al., 2020). Besides, the high dropout rate may also be related to the higher chance of the affected molar to be extracted following advice by an orthodontist during the review phase.

Data Management and Analysis:

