Data obtained will be entered and analysed using Statistical Package for the Social Sciences (SPSS) version 26.0 software. The continuous data will be checked for normality of distribution and reported accordingly. Categorical data in this study are the clinical parameters, clinical outcome, and restorative quality. Descriptive statistics of frequencies and percentages will be presented for categorical data. The primary data analysis will be done using Intention-to-treat (ITT) analysis involving all the samples recruited and randomised. The Per Protocol (PP) analysis will be done to compare the difference between treatment effects as a sensitive analysis of missing value. Comparison of categorical outcomes will be assessed using Chi-square goodness of fit test and Friedman Two-way Analysis of Variance (ANOVA) by Ranks test. Association studies such as factors affecting the outcome will be further evaluated using the Binary Logistic Regression. In all analyses, the level of significance is set at $p<0.05$. The power of the study will be calculated using G*Power Version 3.1.9.4 using the Post Hoc test of Goodness-of-Fit.

Ethical Consideration:

This study has already received approval from the Medical Ethics Committees, Faculty of Dentistry, University of Malaya (CD1912/0061/20155(P)). Patient Information Sheet (PIS) will be disseminated to parents and participated children before consenting. Written informed and verbal consent from parents and, where appropriate, the children, were obtained before intervention. Participation is based on a voluntary basis and they may decide to leave at any time of the study.

Reference:

1. Almualllem, Z. & Busutil-Naudi, A. 2018. Molar incisor hypomineralisation (MIH) – an overview. *British Dental Journal*, 225, 601-609.
4. Gao, S. S., Zhang, S., Mei, M. L., Lo, E. C.-M. & Chu, C.-H. 2016. Caries remineralisation and arresting effect in children by professionally applied fluoride treatment – a systematic review. *BMC Oral Health*, 16.

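### The planned post hoc power figure comes from a goodness-of-fit calculation with unstated inputs, so it does not measure power for the between-arm comparison that the trial is about

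*Combined protocol and SAP*

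**What the plan says.** The Objective is a comparison between the three treatments: "To determine and compare the clinical outcome determine as success and failure of treatment related to pulpal health, structural integrity and hypersensitivity on MIH molars", at 6 and 12 months.

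The Sample size section already contains an a priori calculation. It takes 98.3% success for glass ionomer and an assumed 50% for the new treatments: "With an estimated error of 5% and power of 90%, the minimum estimated sample size was calculated to be 14 teeth per intervention group". The test behind it is one of association: "Pearson chi-square test was used to test the association of two binary variables". The 14 teeth are raised by 50% to 21 per group, 63 in total.

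The Data Management and Analysis section names these tests: "Comparison of categorical outcomes will be assessed using Chi-square goodness of fit test and Friedman Two-way Analysis of Variance (ANOVA) by Ranks test". It then adds a second power calculation, to be run in G*Power "using the Post Hoc test of Goodness-of-Fit". It does not say which outcome, time point, effect size or expected proportions will be entered, or what the result will be used for. The same section plans frequencies, percentages and a binary logistic regression for factors affecting the outcome. It names no confidence interval for a difference between arms.

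**The concern.** There are two separate problems.

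- **The comparison.** Goodness of fit asks whether one set of counts matches fixed shares. It does not ask whether the proportion of successes differs between randomised arms. A power figure from it therefore answers a different question from the one in the Objective and the Sample size section.
- **The timing.** Power computed after the data usually takes the observed effect as its input. It then carries nothing that the p-value does not already carry.

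What is at stake is a number labelled as the power of the study. It could make a clear difference between arms look underpowered, or make a trial with no difference between arms look well powered. With 21 teeth per arm before losses, readers will want to know how precise the result is. An interval for the difference tells them; this figure does not.

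**Working it through.** **Inputs.** From the Sample size section: 98.3%, 50%, 5% error, 90% power, 14 and then 21 teeth per group. My assumptions: the 5% is two-sided, the 50% applies to each of the two new arms, all 21 teeth per arm are observed, and teeth are independent. The expected shares for goodness of fit are not given, so I tried two readings:

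- (A) success counts across the three arms against equal thirds, 2 df;
- (B) pooled success:failure against 50:50, 1 df.

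**Step 1: the plan's own figure.** The two-proportion formula is n = [1.96√(2p̄q̄) + 1.2816√(p₁q₁ + p₂q₂)]² / (p₁ − p₂)². With p₁ = 0.983, p₂ = 0.5 and p̄ = 0.7415 it gives 15.1, so 16 per group. Exact enumeration of the uncorrected two-sided Pearson test gives power 0.901 at 13 and 0.927 at 14 per group. The stated 14 is therefore reproduced to within the choice of method, and 14 × 1.5 = 21.

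**Step 2: design rates entered, 21 per arm.** Power = P(noncentral χ² with noncentrality λ > 5% critical value). The critical value is 3.84 for 1 df and 5.99 for 2 df.

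- Between-arm 3x2 test: mean rate (0.983 + 0.5 + 0.5)/3 = 0.661. λ = 21 × Σ(pᵢ − 0.661)² / (0.661 × 0.339) = 21 × 0.1555 / 0.2241 = 14.6. Power is **0.94**.
- Reading A: shares of successes are 0.496, 0.252 and 0.252. w² = Σ(share − 1/3)² / (1/3) = 0.1187. Expected successes are 21 × 1.983 = 41.6, so λ = 41.6 × 0.1187 = 4.94. Power is **0.50**.
- Reading B: λ = 63 × (0.661 − 0.5)² / 0.25 = 6.53. Power is **0.72**.

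**Step 3: observed effect entered.** Now λ equals the observed χ², so power depends only on p, the significance level and df.

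| p-value | power, 1 df | power, 2 df |
|---|---|---|
| 0.05 | 0.50 | 0.58 |
| 0.01 | 0.73 | 0.78 |
| 0.001 | 0.91 | 0.92 |

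**Step 4: two assumed results, 21 per arm, observed effect entered.**

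*Successes 20, 11, 11.*
- Between arms: χ² = 11.57, p = 0.003, power 0.87.
- Reading A: expected 42/3 = 14 each, χ² = (36 + 9 + 9)/14 = 3.86, p = 0.145, power 0.40.
- Reading B: 42 successes and 21 failures against 31.5 each, χ² = 2 × 10.5²/31.5 = 7.0, p = 0.008, power 0.75.

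*Successes 19, 19, 19.*
- Between arms: χ² = 0, p = 1.
- Reading A: χ² = 0, power 0.05.
- Reading B: 57 to 6, χ² = 2 × 25.5²/31.5 = 41.3, power above 0.999.

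**Step 5: what an interval would show.** For 20/21 against 11/21 the difference is 9/21 = 42.9 percentage points, with a 95% Newcombe interval of 16.5 to 63.2 before any allowance for several teeth in one child.

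**The case against.** The strongest reply has four parts.

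- **The input is not stated.** A reader might infer that the figure must be a restatement of the p-value. The documents do not support that as a certainty, because they never say that the observed effect will be entered. With the design rates entered, the figure is not a function of p. This stands, and the p-value argument is conditional on the usual meaning of post hoc power. The mismatch with the between-arm comparison does not need it, as Step 2 shows.
- **The label may be loose.** Goodness of fit might be a slip for a contingency-table chi-square, and the noncentral chi-square function is the same once λ and df are set. That is possible, so the reported figure may be wrong rather than must be. However, the same section separately names goodness of fit as an analysis test, which makes the literal reading the natural one. On the loose reading the inputs are still unstated, and the p-value argument still applies if the observed effect is used.
- **The power calculation matches the named test.** In the 20, 11, 11 example under reading A, p = 0.145 and power 0.40 agree with each other; the p = 0.003 comes from a test that the section does not name. This is fair. Whether goodness of fit is the right analysis test is a separate issue. The point here is that the figure is offered as the power of the study, whose Objective is a comparison between arms.
- **Little follows from it.** A reader might infer that the figure will steer the trial's conclusions, or that it is the plan's only statement about precision. Nothing in the plan ties interpretation to it, the a priori 90% is stated, and comparing treatment effects between intention-to-treat and per-protocol analyses is mentioned. What remains is narrower: no interval for a between-arm difference is named.

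**Conclusion.** The point holds as a defect of limited consequence. As written, the sentence produces a figure that does not measure power for the trial's own comparison. At the design rates it gives 0.50 or 0.72 where the between-arm test has 0.94. At assumed results it gives 0.40 or 0.75 where the contingency-table figure is 0.87 (20, 11, 11), and 0.05 or above 0.999 where the arms do not differ at all (19, 19, 19). It would be too strong to say that the figure always understates power: the last case shows that it can err upwards, and the size depends on expected shares that the plan leaves open. If the observed effect is entered, the figure also adds nothing to the p-value.

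These numbers rest on a two-sided 5% level, complete data on 21 independent teeth per arm, 50% success in both new arms for the design case, and invented counts for the illustrations. The sentence alters no test, significance level or sample size, so the harm is a misleading reported number. Clustering of teeth within a child is a separate issue and is not quantified here.

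**What to change.** Delete the post hoc power sentence from Data Management and Analysis, and keep the a priori calculation in the Sample size section as the plan's only power statement. In its place, state that the 12-month difference in success proportion will be reported for each pair of arms with a 95% score-type confidence interval (Newcombe's, for example), and that statements about precision will rest on these intervals.

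The cost is a change of wording and a little extra analysis: three differences and their intervals, with no new data. The interval may need software or a short calculation beyond the default output of SPSS 26. If several teeth per child are enrolled, the interval method should follow whatever is decided on clustering.
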